Data analysis	
The primary efficacy variable is the number of Leukocytes (mCL), Neutrophil Leukocyte Ratio, Secretion of COX-2 in blood, Secretion of Endorphin hormones in blood collected at Week 4 to BL (i.e., change from BL in the number of Leukocytes at Week 4). It will be analyzed using wilcoxon signed-rank test or paired t test and Mann-Whitney U test or independent t test. The significance level will be set at 0.05. All outcome measures will be recorded at baseline and after 2 weeks of intervention

Keywords	Osteoarthritis, curcuminoid, acupressure, randomized control trial

1 Introduction

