4.3 Eligibility test procedure

Radiographs will be used to assess participants for Osteoarthritis using the Kellgren and Lawrence criteria which divide Osteoarthritis from mild to severe. It should be remembered that at the beginning of the disease, the radiographic appearance of the joint still looks normal. According to Kellgren and Lawrence, radiologically, osteoarthritis is classified as follows:

- 1) Grade 0: Normal, no signs of osteoarthritis
- 2) Grade 1: Doubtful, without osteophytes, doubtful joint narrowing

3) Grade 2: Minimal, few osteophytes on the tibia and patella and the joint surface is asymmetrically narrowed.

4) Grade 3: Moderate, there are moderate osteophytes in several places, the joint surface is narrowed, and subchondral sclerosis appears.

5) Grade 4: Severe, presence of large osteophytes, complete narrowing of the joint surface, severe subchondral sclerosis, and joint surface damage.

Mini Mental State Examination (MMSE) test will be used to assess the patient's cognitive abilities. This is important to ensure that patients can understand the instructions in the treatment process and the outcome measurement process.

5 Randomization, allocation and blinding

A total of 70 eligible participants will be randomized to the group with curcuminoids capsules and acupressure (C+A; group 1) or the group with placebo and sham acupressure (P+S; group 2) via lottery randomization. Thereafter subjects will be randomly allocated to C+A and P+S group. The schematic CONSORT (Consolidated Standards of Reporting Trials) flow diagram for the study protocol is presented in Figure 1. Schematic CONSORT (Consolidated Standards of Reporting Trials) flowchart for the study.

[figure not shown]

Figure 1. Schematic CONSORT (Consolidated Standards of Reporting Trials) flowchart for the study

Determination of baseline characteristics for every participant will be done by the therapist through a standardized assessment form. During the baseline measurement, the following characteristics will be recorded: sex, age, body mass, pain characteristic, history of disease and medication use. The participant's participation schedule will be determined according to the SPIRIT (Standard Protocol Items: Recommendations for Interventional Trials) statement Figure 2. The primary and secondary outcome measures will be recorded before providing the intervention.

[figure not shown]
TIMEPOINT**	STUDY PERIOD								
	Enrolment	Allocation	Post-allocation			Close-out			

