The patient is observed for a local twitch response. The patient is asked to report any abnormal sensations or discomfort during the course of intervention.

The sponsor will provide double-blind study medication for Curcuminoid and Placebo

Preparation of standardized curcuminoid turmeric extract preparations. Samples were made from extracted turmeric and then optimized. The capsule formulation is made from turmeric rhizome extract which contains 30 mg of curcuminoids per capsule. In the study, standardized curcuminoid turmeric extract was given in capsules at a concentration of 30 mg 3 times a day for 3 weeks.

7 Outcomes

All outcome measures will be assessed at baseline and after 3 weeks of intervention.

Primary Outcomes measures

1) Inflammatory Markers

Inflammation markers are carried out by measuring leukocyte numbers and the Neutrophil Lymphocyte Ratio. The examination is carried out using a complete blood test using a Hematology Analyzer, which is a laboratory tool used to measure and count the number of blood cells. The blood samples are mixed using a mixture of reagents to create a process called hemolyzing. This process will be divided into several purposes, to measure leukocytes, neutrophils, platelets and erythrocytes.

2) Secretion of the COX-2 hormone

The enzyme cyclooxygenase-2 (COX-2) is an important mediator in increasing the inflammatory response. In the blood plasma of patients with osteoarthritis, the COX-2 enzyme can be detected. The COX-2 hormone examination was carried out using the Enzyme Linked Immunosorbent Assay (ELISA) method on blood plasma.

3) Secretion of endorphin hormones

Endorphins, in this case beta endorphin, are hormones released by the pituitary gland in response to stress or pain, which are also secreted in blood plasma. Endorphin hormone levels in the blood were measured before starting therapy and after 3 weeks of therapy.

Endorphin hormone examination is carried out using the Enzyme Linked Immunosorbent Assay (ELISA) method on blood plasma that has been incubated at room temperature for 10-20 minutes, then the tube will be centrifuged for 20 minutes at a speed of 2000-3000 rpm.

Secondary outcomes

The effectiveness of therapy is the ability of the therapy regimen given to suppress several other expected output indicators. Other output indicators were measured before starting therapy and after 3 weeks of therapy

1) Knee pain as measured by the VAS score

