9.3 Data analysis

The data collected will be analyzed by the secondary researcher. Descriptive statistics will be used to evaluate the baseline characteristics of participants. The normality of the collected data will be established using the Shapiro–Wilk test. Based on data normality, descriptive statistics will be expressed as mean \pm standard deviation or median (interquartile range). Within-group comparisons will be conducted using the Wilcoxon signed-rank test or a paired t test. Similarly, the Mann–Whitney U test or an independent t test will be used for between-groups comparisons. The level of significance will be set at 0.05.

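### The between-arm tests make no covariate use of the recorded baselines; a prespecified ANCOVA on a named scale would be more precise at almost no cost

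*Combined protocol and SAP*

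**What the plan says.** The Data analysis row of the protocol summary defines the primary variable as change from baseline and continues: "It will be analyzed using wilcoxon signed-rank test or paired t test and Mann-Whitney U test or independent t test". Section 9.3 gives the same choice for comparing arms (Mann-Whitney "U test or an independent t test will be used for between-groups comparisons") but does not say whether change or the 3-week value is compared. The only rule about distribution is also in 9.3: "The normality of the collected data will be established using the" Shapiro–Wilk test. No regression model, covariate, transformation or confidence interval is mentioned for this trial. The covariate adjustment described in section 1.1 belongs to a cited acupressure study.

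The baseline data exist. Section 5 states: "The primary and secondary outcome measures will be recorded before providing the intervention". Section 7 states: "All outcome measures will be assessed at baseline and after 3 weeks of intervention". The primary markers are blood cell measures ("Inflammation markers are carried out by measuring leukocyte numbers and the Neutrophil Lymphocyte Ratio") and two plasma ELISA levels, COX-2 ("The COX-2 hormone examination was carried out using the Enzyme Linked Immunosorbent Assay (ELISA) method on blood plasma") and beta endorphin ("Endorphin hormone levels in the blood were measured before starting therapy and after 3 weeks of therapy").

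**The concern.** Baseline enters the summary's analysis only by subtraction, and under one reading of 9.3 it does not enter at all. Subtraction is the best use of baseline only when the regression slope of follow-up on baseline is 1. Ignoring baseline is best only when the slope is 0. ANCOVA estimates the slope and so does at least as well as either, apart from one degree of freedom.

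The trial is small: 70 randomised with 20% dropout leaves about 56 patients, or 28 per arm. At that size a loss of precision matters.

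The scale matters too. Counts, ratios and ELISA levels are positive and often right-skewed, although the documents give no distribution for them. If the scale is left to a normality test on the trial's own data, the primary test is not fixed in advance.

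**Working it through.** **Inputs.** 70 randomised (section 5), equal allocation assumed, 20% dropout (section 8): 70 × 0.8 / 2 = 28 per arm. Two-sided 5%, since section 8 uses z = 1.96. The baseline-to-follow-up correlation rho is not in the documents; 0.3, 0.5, 0.7 and 0.8 are assumed.

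**The plan's own figure.** Section 8: 2 × 14.01² × 2.802² / (174.27 − 164.1)² = 3082.07 / 103.43 = 29.80, i.e. 30 per arm. This reproduces.

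**Variance ratios.** With unit variance at both visits, the per-patient variance is 2(1 − rho) for change, 1 for the 3-week value, and 1 − rho² for ANCOVA. Hence:

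- ANCOVA / change = (1 − rho²) / (2(1 − rho)) = (1 + rho)/2
- ANCOVA / 3-week value = 1 − rho²

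**Power at 28 per arm, assumed effect 0.6 SD of the marker.** Noncentral t: 54 df for the unadjusted tests; 53 df for ANCOVA, averaged over chance baseline imbalance.

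| rho | ANCOVA/change variance | ANCOVA/3-week variance | Power, change | Power, 3-week value | Power, ANCOVA |
|---|---|---|---|---|---|
| 0.3 | 0.65 | 0.91 | 0.46 | 0.60 | 0.63 |
| 0.5 | 0.75 | 0.75 | 0.60 | 0.60 | 0.71 |
| 0.7 | 0.85 | 0.51 | 0.81 | 0.60 | 0.86 |
| 0.8 | 0.90 | 0.36 | 0.94 | 0.60 | 0.95 |

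For an assumed 0.4 SD, change to ANCOVA is 0.24 to 0.33, 0.31 to 0.39, 0.48 to 0.53 and 0.64 to 0.68.

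**Cost of the extra term.** With 56 patients the variance rises on average by a factor 1 + 1/52 = 1.019. ANCOVA therefore still gains over change unless rho exceeds 2/1.019 − 1, about 0.96. It gains over the 3-week value unless rho is below √(1 − 1/1.019), about 0.14.

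**At the plan's own effect.** 10.17 / 14.01 = 0.73 SD of change. Power is 0.76 for change and 0.91, 0.86, 0.82 and 0.80 for ANCOVA. However, 14.01 = (78.93 − 50.91)/2, half the difference between the two SDs quoted in section 8. Their root mean square is √((50.91² + 78.93²)/2) = 66.4, so the effect is 10.17 / 66.4 = 0.15 SD. Power is then about 0.09 for change and 0.09 to 0.11 for ANCOVA.

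**Scale (simulation, illustration only).** Lognormal markers, effect 0.6 SD on the log scale. The planned route was read as Shapiro–Wilk on change in each arm, then Mann-Whitney if either rejects, otherwise t. With log-SD 1, power for planned route / raw ANCOVA / log ANCOVA / rank ANCOVA was:

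- 0.41 / 0.50 / 0.71 / 0.68 (rho 0.5, downward effect)
- 0.77 / 0.62 / 0.86 / 0.83 (rho 0.7, upward effect)

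In the second case raw-scale ANCOVA is worse than the planned route, so adding baseline without naming a scale is not enough. Rejection under the null was 0.040 to 0.055 for all four methods.

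**If log is the wrong scale.** For a truly normal marker with CV 0.3 and a downward effect, raw versus log ANCOVA gave 0.620 / 0.573, 0.714 / 0.666 and 0.865 / 0.821 at rho 0.3, 0.5 and 0.7: a loss of about 0.05. Against the planned route, log ANCOVA was above or level up to rho 0.7 and at most about 0.03 below at rho 0.8. Trials with near-zero values (4–14%) were discarded. Logging does worst in those trials, so the loss may be somewhat understated.

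**The case against.** The strongest reply is that this is an efficiency preference. The planned tests are valid, the summary already uses baseline by analysing change, and at rho 0.7 to 0.8 the normal-theory gain over change is only 0.01 to 0.05 of power. That stands as a limit on size. It does not remove the gain, and if 9.3 means the 3-week value, high rho is where the gain is largest.

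The documents give neither rho nor any marker distribution. That also stands. The lognormal gains over the planned route (up to 0.31 in the cells run) come from data generated under the log-ANCOVA model itself, so they illustrate an assumption and say nothing about these markers. The variance ratios in the table do not need skewness.

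A reader might infer from section 1.1 that the markers will fall, and that change scores would then lose most. The curcuminoid study described there concerns synovial fluid, whereas this trial measures blood, so no direction of effect can be taken from it. A reader might also infer that the planned tests inflate type I error. Nothing in the documents or in the null simulations supports that.

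**Conclusion.** The point holds as a recommended improvement in precision. No planned between-arm test uses baseline as a covariate, the baselines are collected anyway, and ANCOVA is more precise than either reading of the plan over rho 0.3 to 0.8. The saving in variance is 35% to 10% against change and 9% to 64% against the 3-week value. These figures assume equal variances at the two visits, 28 per arm and the stated range of rho. The log scale is a reasonable default for positive markers, but no figure in the documents supports it.

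It would be tempting to conclude that ANCOVA restores the trial's power. It does not: with the SDs quoted in section 8, power stays near 0.1 whichever analysis is used. The sample-size SD is a separate matter.

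**What to change.** In section 9.3 and the protocol summary, prespecify as the primary between-arm analysis an ANCOVA of the 3-week value on arm and baseline value. Apply it to the four markers that the summary's analysis row and section 7 share: leukocytes, neutrophil ratio, COX-2 and endorphin.

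- Fix the scale before unblinding, and not by the Shapiro–Wilk result.
- Use logs for outcome and baseline, and report the adjusted ratio of geometric means with a 95% confidence interval.
- Name rank ANCOVA in advance for any marker where logs are not usable, for example because of values below the assay limit.
- Keep the planned test on change as a sensitivity analysis, and state in 9.3 that change is the quantity it compares.

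Section 2.1 also lists sedimentation rate and pain in the primary objective. If they stay there, each needs its own named scale; logs do not suit a pain score that can be zero. The conflicting assessment times in the summary need to be reconciled separately.

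The cost is a few sentences and one regression per marker, with no new data or visits. The downsides are one degree of freedom per model, an effect expressed as a ratio, and about 0.05 less power than raw-scale ANCOVA if a marker is truly normal with CV 0.3.

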1.1 Background

One of the degeneration processes that occurs in the elderly is the musculoskeletal system. These deteriorations include bone loss and a decrease in joint fluid volume which is exacerbated by bearing the weight of the body. This deterioration causes elderly people to experience pain. The experience of prolonged pain in Osteoarthritis patients becomes a “Breakpoint ” which centers on the experience/process of living with unremitting pain, limitations in mobility, leisure and social activities, and the resulting consequences for the patient's physical and psychological well-being . The breakpoint experienced by Osteoarthritis patients is the turning point for changes in quality of life in Osteoarthritis. Popular alternative therapies include herbal therapy, therapeutic touch, relaxation techniques, music therapy, acupuncture, and acupressure. One of the therapies that is very close to the community, especially the Javanese, is acupressure, which is a further development of massage. Until now, massage is an action that people often do independently and can psychologically make patients feel comfortable, but research needs to continue to be carried out to ensure its effectiveness.

Pain in Osteoarthritis patients affects many areas of quality of life such as physical function, emotional behavior, and mental health. Osteoarthritis-related pain is a major factor in poor quality of life. The most common pharmacological treatment to control pain is the use of non-steroidal anti-inflammatory drugs (NSAIDs), but these drugs carry the risk of causing side effects. Limitations associated with pharmacologic treatment result in patients choosing commonly available alternative therapies for pain management. Popular alternative therapies include herbal therapy, therapeutic touch, relaxation techniques, music therapy, acupuncture, and acupressure. This alternative therapy, unlike the use of drugs, does not produce dangerous side effects. (Li et al., 2018)

Research on the effectiveness of herbal therapy on inflammatory osteoarthritis patients was conducted in Indonesia by [name] in 2009 on 80 sufferers with the result that administration of turmeric rhizome extract curcuminoids significantly suppressed the activity of synovial fluid monocytes to secrete COX-2 and ROI, reduced leukocyte numbers and fluid MDA levels. synovial fluid and reduces OA joint pain, with an ability that is not significantly different compared to diclofenac sodium therapy 3x25 mg per day ([name], 2009). Furthermore, the development of herbal therapy for Osteoarthritis continued with research by Bertorio (Bertorio, 2017) which proved that the combination of ginger, ginger, soybean and shrimp shell extracts provided significant results in reducing joint pain, stiffness and physical disability which were evaluated based on the Western Ontario and McMaster values. Universities Osteoarthritis Index (WOMAC) and did not show a significant difference when compared with meloxicam.

Research that has been carried out to evaluate the effectiveness of acupressure therapy for the pain of Osteoarthritis patients was also carried out in several countries, including by Alinaghizadeh on 40 Osteoarthritis patients who were divided into two groups (intervention and control). In the intervention group, acupressure therapy was given for 5 days with a duration of 30 minutes each time. The results showed that the average pain score in the intervention group decreased significantly from 5.89 at the beginning of the study to 4.11 at the end of the study, while the pain score did not change substantially in the control group. These findings remained consistent after adjusting for age, weight, and pretreatment covariates. This study supports the evidence that Acupressure therapy provides an effective option for short-term knee pain relief in patients with knee Osteoarthritis. (Maryam Alinaghizadeh et al., 2021). In line with the results of Alinaghizadeh's research, there was research conducted by Akbarnezhad (Akbarnezhad et al., 2019) which was conducted on 51 elderly with osteoarthritis divided into 3 groups (acupressure intervention, placebo and

control). This study revealed that respondents who received acupressure therapy for 3-4 weeks with the duration of each therapy being 10-15 minutes, showed a significant reduction in the total WOMAC index, pain and physical dysfunction.

So far, there has been no research combining standardized curcuminoid turmeric extract therapy with acupressure for inflammation and pain in osteoarthritis patients. More clinical trials with appropriate methodology are needed to confirm the effectiveness of standardized turmeric extract, curcuminoids and acupressure to treat physical problems in osteoarthritis patients.

1.2 Purpose

To investigate the efficacy of acupressure and standardized curcuminoids from turmeric extract to inflammatory markers, endorphin hormones in the blood and quality of life in elderly patient with Osteoarthritis Genu.

2 Study objectives and endpoints

2.1 Primary objective

To determine the effectiveness of combination two regimens (acupressure and curcuminoid) as measured by changes from baseline (BL) in Leukocytes, Neutrophil Leukocyte Ratio, Blood Sedimentation Rate, Pain, secretion of COX-2 and Endorphin hormones in blood to placebo after 3 weeks of treatment in elderly patients with Osteoarthritis

2.2 Secondary objectives

To evaluate the effect of acupressure and standardized curcuminoid from turmeric extract vs placebo at 3 weeks is Quality of Life that were measured by Respondents' satisfaction in carrying out daily activities based on indicators on the *Knee injury and Osteoarthritis Outcome Score (KOOS)* instrument

3 Investigational plan

3.1 Study design

Randomized controlled trial, we will conduct a 2-arm, double-blind (patient and investigational blinded) to assess efficacy, tolerability and safety combination of acupressure and curcuminoid versus placebo.

Pre-Screening:

Patients can be pre-screened for certain x-ray and laboratory parameters. Following a screening visit, eligible subjects will enter the wash-out. After the wash-out period, eligible subjects will be randomized and treated for 3 weeks. The total duration of the study is up to 5 weeks.

3.2 Study setting and source population

Eligible participants were individuals recruited from communities covered by government-owned primary care hospitals who consulted a rheumatology subspecialist physician with symptoms of pain and discomfort around the knee.

Participants will be recruited from August 2023 to September 2023. An informed-consent form will be provided to participants in their local language to gain credibility. Codes will be assigned to ensure confidentiality for data collection, with only the primary researcher having access to the participant codes for each group. Participants providing their consent will be further screened for eligibility.

4 Population

The study population will consist of male and female patients (≥ 65 years old) with Osteoarthritis (Osteoarthritis with knee joint pain, knee joint stiffness in the morning less than 30 minutes, Crepitus, deformity, joint swelling (right and left asymmetrical), Other signs of inflammation (a feeling of even warmth and reddish color). The goal is to randomize a total of approximately 70 patients. Since a 25% screening failure rate and a 20% washout failure rate is expected, approximately 100 patients will be screened.

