Secondary Objectives	To evaluate the effect of acupressure and standardized curcuminoid from turmeric extract vs placebo at 3 weeks : 
 • Knee pain as measured by the VAS score • Joint stiffness and joint functional ability are assessed by the WOMAC score • The independence of the elderly as assessed by the Barthel Index • Quality of Life were measured by Respondents' satisfaction in carrying out daily activities based on indicators on the KOOS instrument
Study design	Randomized controlled trial, double-blind to assess efficacy, tolerability and safety combination of acupressure and curcuminoid versus placebo. Patients can be pre-screened for certain x-ray and laboratory parameters. Following a screening visit, eligible subjects will enter the wash-out for 1 week. After the wash-out period, eligible subjects will be randomized and treated for 3 weeks. The total duration of the study is up to 5 weeks
Population	Approximately 70 female and male patients ≥ 65 years old
Key Inclusion criteria	
 • Clinical diagnosis of osteoarthritis which confirmed by physical examination and x-rays • Experience pain with a Numeric Rating scale of 1-7 • Must be able to swallow capsules • Must be able to carry out mobility without assistance or with minimal assistance

Key Exclusion criteria	
 ● Parkinson's disease ● Dementia disease ● Psychosis disease ● New bone fractures ● Joint dislocations ● Cancer ● Rheumatic diseases other than osteoarthritis (rheumatoid arthritis) ● Undergoing joint replacement therapy. ● Analgesic dependent disease
Study treatment	
 ● Combination of Acupressure and Curcuminoid from turmeric extract ● Placebo
Efficacy assessments	
 ● Leukocytes ● Neutrophil Leukocyte Ratio ● Blood Sedimentation Rate ● Pain ● Secretion of COX-2 in blood ● Secretion of Endorphin hormones in blood
Key safety assessment	
 ● Physical examination ● Vital signs ● Monitoring of laboratory markers in blood
Others assessment	
 ● Quality of Life

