9.4 Data management

Data collected will be kept confidential throughout the study duration and will be discarded after 5 years. Initial documentation of data will be performed through printed data-collection forms, which will later be managed and transcribed into electronic format and stored on a desktop computer without an internet connection (to help prevent unauthorized data access) for further analysis. Data will be overseen by the chair of the student project committee of the institute

10. Ethical considerations

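### The primary researcher alone holds the participant codes for each group, so the investigator blinding stated in Section 3.1 does not hold for that person as written

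*Combined protocol and SAP*

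**What the plan says.** The Protocol summary describes the study as "Randomized controlled trial, double-blind to assess efficacy, tolerability and safety combination of acupressure and curcuminoid versus placebo" without naming the blinded parties. Section 3.1 names them: "double-blind (patient and investigational blinded".

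Section 3.2 introduces codes in its account of recruitment and consent: "Codes will be assigned to ensure confidentiality for data collection". The same sentence continues: "with only the primary researcher having access to the participant codes for each group".

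Section 5 says what a group is. Group 1 receives curcuminoid capsules and acupressure. The alternative is "or the group with placebo and sham acupressure (P+S; group 2) via lottery randomization". The title of that section is "5 Randomization, allocation and blinding", but the text gives no blinding procedure, code custodian or unblinding rule.

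Three other places bear on the point:

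- Section 6, on the capsules: "The sponsor will provide double-blind study medication for Curcuminoid and Placebo".
- Section 9.3 gives the analysis to the secondary researcher and does not say whether that person is blinded.
- Section 9.4, on oversight: "Data will be overseen by the chair of the student project committee of the institute". It does not mention custody of the codes.

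**The concern.** One rule in the plan conflicts with a property that the plan claims for its design. A lead researcher who can look up each participant's arm is not blinded, whatever the capsules look like.

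The stake is the credibility of the comparison between arms. Pain is part of the primary objective in Section 2.1. VAS pain, WOMAC, the Barthel Index and KOOS are secondary outcomes in Section 7. These are reported or rated measures, which are in principle open to expectation and encouragement. The blood measures are less exposed at the moment of measurement. Section 9.3 defines no analysis population and no rule for missing data, so decisions on individual records are not tied down in advance. A report that called the trial investigator-blinded without qualification would also not match the procedure in Section 3.2.

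**Working it through.** No arithmetic applies, and the plan gives no figure to reproduce. The check sets the sections side by side.

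1. **Who is said to be blinded?** Section 3.1 names the patient and a second party in garbled wording. The natural reading of the second party is the investigator. This is an inference, though a modest one.
2. **Who has the codes?** Section 3.2 gives access to the primary researcher and to nobody else.
3. **What do the codes show?** Section 3.2 gives confidentiality as their purpose and does not call them allocation codes. It does, however, describe them as being for each group.
4. **What is a group?** In Section 5, group 1 is the active combination and group 2 is placebo with sham. Participant codes kept by group therefore separate the participants by arm.
5. **When could the codes show this?** Section 3.2 mentions the codes before eligibility screening is complete. Section 3.1 places randomisation after screening and wash-out. A code issued at consent cannot yet carry an arm. Once participants have been randomised, a key organised by group does.
6. **Does another section separate the primary researcher from the key?** Section 5 names a lottery but no independent holder. Section 6 covers the supply of blinded capsules, which does not blind someone who has the group key. Section 9.3 names the analyst and Section 9.4 the overseer of the data. Neither takes the key away from the primary researcher.

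Steps 2 to 4 put each randomised participant's arm within reach of the primary researcher. Step 1 says that the investigator is blinded. Step 6 finds nothing that reconciles the two.

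**The case against.** The best defence is that the codes are an identification key. Their stated purpose is confidentiality, they appear in the text on consent and screening, and one loose phrase about groups may be bearing too much weight. This defence has some force and limits how firmly the conflict can be stated. It does not remove the need for an edit. A pure identity key has no need to be arranged by group. If an identity key was nevertheless meant, the protocol names no holder of the allocation list at all.

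A second objection concerns consequences, and most of it stands. A reader might infer that the primary researcher could enrol selectively. That requires knowing the next assignment, which a list of past assignments does not give by itself. Section 4.2 also bars the investigator from adding exclusions. The mechanics of the lottery are not described, so the question is open, but it concerns allocation concealment and is not shown by the custody of this list.

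A reader might also infer that outcomes are assessed or analysed with knowledge of the arm. No section says that the primary researcher treats or assesses anyone or decides on exclusions. Section 5 has the therapist record baseline characteristics, and Section 9.3 has the secondary researcher analyse the data. Patient-reported scores come from patients who are stated to be blinded.

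A third objection is that moving one list would not settle the double-blind claim, because the plan does not say whether the therapist giving acupressure or sham is blinded. This is right, and the fix has to cover it.

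**Conclusion.** As written, the stated blinding does not hold for the primary researcher. The conclusion rests on two readings: that the garbled phrase in Section 3.1 means the investigator, and that codes for each group distinguish the arms that Section 5 defines. Both are the natural readings, but neither is certain, so confidence is medium.

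The list would cover every randomised participant, approximately 70. The effect on any outcome cannot be estimated from the documents. What is supported is a possible influence on conduct, follow-up and data handling by one person who knows the arms. It would go too far to say that assessment or analysis is unblinded, that enrolment is affected, or that patient blinding has failed. The change should be made because it is easy and removes a contradiction in the plan, not because bias has been demonstrated.

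**What to change.** - Amend Section 3.2 so that the code-to-arm list is held until database lock by an existing person with no role in enrolment, treatment, assessment or analysis, with a documented route for emergency access.
- Confirm that person's independence before naming them. The capsule supplier and the committee chair in Section 9.4 are obvious candidates, but neither is shown to qualify: the sponsor is the investigators' own university, and the chair already oversees the data.
- Have the primary and secondary researchers work only with participant numbers and masked arm labels such as A and B.
- State in Section 5 which roles are blinded, including whether the therapist delivering acupressure or sham is.
- If custody cannot be moved, restate the blinding claim in the Protocol summary and Section 3.1 so that it excludes the primary researcher.

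The cost is a short text amendment, with the approval that Section 11.1 requires, and a change of custodian for one list. No added staff or data collection is needed.
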